- c. **Patient Navigation (PN):** phone call from a community health worker to help address hesitancy and access barriers, and to offer at-home rapid test kits. Two types of PN will be tested: **Request PN** (RPN) will contact only those patients who reply YES to a TM/CA message. No PN will have no contact from a patient navigator.

Prior to randomization, patients will be triaged into one of two studies based on self-reported ownership of a smart phone with internet access.

The primary outcome, Testing, captures whether patients actually test with the mailed at-home test kit.

Secondary outcomes include: *Time-To-Vaccine* (time-to-event outcome) as well as several implementation outcomes including *Reach-Engage Testing* (proportion of patients that reply to an offer to receive an at-home rapid test kit) and *Reach-Accept Testing* (proportion of patients that accept an offer to receive an at-home test kit). A similar set of implementation outcomes will be measured for vaccination (i.e., *Reach-Engage Vaccine* and *Reach-Accept Vaccine*).

8. Background and Introduction:

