SCALE-UP Utah II is composed of two experimental studies, which allow participants access to COVID-19 testing and/or vaccine resources via technology-based interactive platforms. Participant cohorts will be selected from the electronic medical records pulled from the participating community health centers. Minors (under 18) will be included in the data pull, however people under the age of 18 will not be included in any of the following interventions (IE: text messages, conversational agents, patient navigation, or surveys). Their information is included to allow for parents to request COVID tests for their children. Children will not be contacted by the study for any reason. Due to this lack of any direct contact, the study is utilizing an "assent waiver" for children under the age of 18.

Participants will be triaged into one of the two designs based on self-reported smart phone access. Individuals who report using a smart phone will be placed in the Conversation Agent (CA) study /Text Message (TM) study and subsequently be randomized between either a CA or TM arm. Individuals who report they do not use a smart phone or do not respond within a certain timeframe, will be placed in the Text Message (TM) Only study. Both studies will stratify the population between two different levels of patient navigation (PN). Patient Navigation will consist of a patient navigator calling participants who request a call from a PN. Patients will be randomly assigned to either No PN or Request PN (RPN).

The CA study will utilize a customized conversational agent platform, which is HIPPA compliant to provide patients with an interactive, dynamic experience to reach COVID-19 testing and/or vaccine resources.

The TM Only study will use a bi-directional text messaging platform to send patients messages about COVID testing and/or vaccination. The message response logic is based on the patient's responses to the messages. The answer options for patients will be simple and allow patients to STOP the intervention at any time.

Within the Conversation Agent (CA) study and the Text Message Only (TM) study, patients will be randomized to one of two patient navigation arms: No PN or Request PN (RPN). Patients randomized to No PN, will not be connected by a patient navigator. Patients randomized to RPN will only be called if they request a call by replying PERSON to a text message.

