In RPN patient navigators will assist patients address barriers in engaging in COVID-19 testing and/or vaccination.

Population Health Management Interventions:

SCALE-UP Utah II will build on the standing partnerships among the University of Utah Clinical and Translational Science Institute, Association for Utah Community Health (AUCH), Community Health Centers across the state, and the Utah Department of Health (UDOH); and will leverage infrastructure enabled in SCALE UP Utah I. Hence, we have agile infrastructure, collaborations, and processes that are "shovel ready" to support novel, practical and scalable PHM interventions to increase COVID-19 testing and vaccination among Utah CHC patients.

The study team's primary outcome, Testing, captures whether patients complete at-home tests that were requested through the study.

The secondary outcomes, Time-To-Vaccine (time-to-event outcome) as well as several implementation outcomes including Reach-Engage Testing (proportion of patients that reply to an offer to receive an at-home rapid test kit) and Reach-Accept Testing (proportion of patients that accept an offer to receive an at-home test kit). A similar set of implementation outcomes will be measured for vaccination (i.e., Reach-Engage Vaccine and Reach-Accept Vaccine).

This experimental aims are:

- a. Conducting a 2 (TM vs. CA) X 2 (No PN vs. RPN) factorial design assessing intervention effects on testing outcome. The study team hypothesizes a main effect for CA being more effective than TM Only, and a main effect for PN, comparing RPN vs. No PN (RPN > No PN).
- b. Conducting a 2 arm (No PN vs. RPN) trial among a subset of participants who receive only text messaging (no chatbot). The study team hypothesizes a main effect for PN, comparing RPN vs. No PN (RPN > No PN).
- c. Examining factors associated with at-home testing and/or vaccination uptake over the life of the study. The study team will assess predictors of outcomes and moderators of intervention effects, such as characteristics of patients and contextual factors related to the status of the pandemic.

Text Message Only Study

Overview:

The Text Message Only Study is comprised of participants who either do not answer the original screener question regarding smart phone use or answer that they do not use a smart phone.

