Patients in the Text Message Only design will be randomized between two different conditions; TM only (no PN) and TM+ RPN. Patients in the TM only condition will receive HIPAA-compliant bidirectional text messages. Texts will include a brief message regarding COVID-19 testing and/or vaccination information. Patients who reply "yes" will

receive additional messages with a recommendation to be tested in-clinic or at home and/or vaccinated. Additionally, they will receive in-clinic testing and/or vaccination locations/hours/phone and/or patient will be able to request an athome testing kit, based on participating clinic involvement. At-home test kits are FDA approved, free of cost to the participant, and sent on behalf of the participants' clinic. Patients who reply "no" may receive a text with the clinic phone number and a note to call if anything changes. Patients in this No PN condition will not receive any PN phone calls

Patients in the TM+RPN condition will receive the same text messages and testing/vaccination options as the patients in the TM only condition. Patients randomized to TM+RPN will be given the option to request a call by replying PERSON to a text message.

Conversational Agent / Text Message Study

Overview:

The Conversational Agent/Text Message Study is comprised of patients who answer the original screener question regarding smart phone use affirmatively, meaning that they do use a smart phone.

Patients in the Conversational Agent/ Text Message Study will be randomized into two different arms; 1) Conversational Agent (CA) and 2) Text Message No Conversational Agent (TM- No CA).

The TM- No CA group will receive HIPAA-compliant bidirectional text messages, just like the message sent to the participants in the TM Only Study. Patients will be randomized between two different conditions: TM - No CA (no PN) and TM+RPN.

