Throughout the course of the study, on a quarterly basis, the study team will send identifiable patient data and study outcomes to project's sponsor, The National Institutes of Health. The identifiable information being transferred will include the CDE portion of the survey. This process will be detailed and approved through data transfer agreements involving the community health centers, the Association for Utah Community Health, The University of Utah Office of Sponsored Projects, The University of Utah IRB, and Duke University, which is housing the data for the National Institutes of Health.

● Yes ○ No		• .		·	ŕ	
If no list the n	rocedures that are n	erformed for res	search nurnoses onl	v (non-standard o	r non-stand	1:

7. Are all procedures for research purposes only (non-standard or non-standard of care procedures)?

If no, list the procedures that are performed for research purposes only (non-standard or non-standard of care procedures):

8. Is there a safety monitoring plan for this study?

Yes No

9. Provide a summary of the statistical methods, data analysis, or data interpretation planned for this study. Factors for determining the proposed sample size (e.g., power) should be stated.

We will conduct two randomized clinical trials: RCT 1 includes participants who affirm they have a smart phone and RCT 2 includes all other participants. We will perform two categories of statistical analyses: 1) Comparing the main effects of TM vs. CA (RCT 1), main effects of RPN vs. no PN (RCT 1 and 2 combined), interaction effects (RCT 1), and follow-up pairwise comparisons of the study arms (RCT 1 and 2); and 2) Evaluating predictors of outcomes and moderators of intervention effects (RCT 1 and 2).

Primary Analyses of Testing for TM vs. CA and no PN vs. RPN. Alpha will be set at 0.0167 to maintain a family-wise error rate of 0.05 across the three primary hypotheses comparing treatment arms. We will apply generalized estimating equations to implement a repeated measures logistic regression to relate the probability of receiving a COVID-19 test within a shorter time frame to the randomized treatment group. Robust sandwich variance estimates will be utilized to account for dependencies between potential repeated observations on each subject (i.e. several potential time-intervals post-randomization where patients might test).

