## SCALE-UP Utah II: Community-Academic Partnership to Address COVID-19 Text

Messaging Study

9/5/2024

NCT05533918

The primary hypotheses for the Smartphone study were main effects for delivery mechanism (Chatbot > TM), main effects for PN (PN > No PN), and main effects for message frequency (10-day > 30-day). For the non-Smartphone study, the primary hypotheses were main effects for PN (PN > No PN) and main effects for message frequency (10-day > 30-day). These hypotheses were adjusted for multiple comparisons using the Bonferroni method at an alpha of .0167 for the Smartphone study to account for three coprimary comparisons, and .0250 for the non-Smartphone study to account for two coprimary comparisons.

Separate analyses were conducted for the Smartphone study and the non-Smartphone study. Log-binomial models were used to regress *Reach-Accept Testing* upon each of the three main effects in the Smartphone study, i.e. Chatbot (vs. TM), PN (vs. No PN), and outreach frequency (10 vs. 30 days); and two main effects in the non-Smartphone study, i.e. PN (vs. No PN) and outreach frequency (10 vs. 30 days). The log-binomial models included covariates to adjust for randomization stratification variables (rural vs. urban, CHC, randomization arm in our previous SCALE-UP I trial) and a categorical variable reflecting the calendar month when the participant received the first intervention message. Adjusted risk ratios (aRR) and confidence intervals were reported for each main effect. In preliminary analyses reported in the Online Supplement, the pairwise and 3-way interactions between the main effects were added to the log-binomial models described

above in order to assess for any effect modifications across interventions, but these analyses did not support the inclusion of the interactions.

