We preliminarily estimated a model specification including the pairwise and 3-way interactions between the main effects and the smartphone ownership indicator in order to assess for any synergistic and/or antagonistic effect modifications across interventions. We have conducted these analyses for the primary outcome (Reach-Accept Testing) for both the smartphone and non-smartphone groups. In both analyses, the estimated coefficients on all interaction terms were not statistically significant at the 5% level. We have conducted an omnibus test (using the car::linearHypothesis function in R) and found that in each case, these coefficients were jointly not statistically significant.

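### RCT 2 combines patients who answered no to the smartphone screener with those who did not answer it, so the SAP's non-Smartphone results cannot be read as specific to people without smartphones

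*Protocol*

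**What the plan says.** **Protocol.** Section 4 (Study Information), item 6, sets the triage rule: "Individuals who report they do not use a smart phone or do not respond within a certain timeframe, will be placed" in the Text Message Only study. The overview of that study repeats it, describing "participants who either do not answer the original screener question regarding smart phone use or answer that they do not use a smart phone". Item 9, on statistical methods, agrees: "RCT 1 includes participants who affirm they have a smart phone and RCT 2 includes all other participants". Entry to the other study is open only to "patients who answer the original screener question regarding smart phone use affirmatively, meaning that they do use a smart phone". The purpose section gives a shorter account without the default: "patients will be triaged into one of two studies based on self-reported ownership of a smart phone with internet access". The length of the reply window is not given. Under Step Three of item 6, randomisation to arms follows triage.

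**SAP.** The group becomes the non-Smartphone study, with its own models and two coprimary hypotheses (navigation and message frequency), each tested at 0.0250: "For the non-Smartphone study, the primary hypotheses were main effects for PN (PN > No PN". The closing paragraph on interactions refers to an indicator of smartphone ownership and says the checks on the primary outcome were run "for both the smartphone and non-smartphone groups". The SAP does not mention that non-repliers are included. Its covariates are rural or urban location, CHC, arm in the previous trial, and calendar month of first message. Screener response is not among them, and no result is planned by screener response.

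**The concern.** A patient who does not answer the screener has reported nothing about ownership. Eligibility (Protocol section 3, item 5) asks only for a working cellphone, so such a patient may well own a smartphone. The SAP's label nevertheless describes the whole group by lack of a smartphone.

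This matters more here than a loose label usually would. The SAP's primary outcome, Reach-Accept Testing, is acceptance of a kit offer. In the text-message pathway a kit request follows a reply, and so does the navigator call. Triage therefore sorts patients partly on responsiveness, which both the outcome and the navigation intervention depend on. Two readings are at risk:

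- A navigation or frequency effect in RCT 2 could be attributed to people without smartphones when much of it comes from patients who did not answer the screener.
- A difference between the two studies could be attributed to ownership when it partly reflects readiness to reply.

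The Chatbot comparison in RCT 1 likewise concerns patients who answered the screener and said yes, not smartphone owners in general.

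**Working it through.** **The plan's own figures.** 0.05 / 2 = 0.0250 and 0.05 / 3 = 0.0167, as the SAP states. 43,325 × 0.85 × 0.80 = 29,461, which matches the protocol's approximate 29,500 for randomisation. None of these figures is affected. The documents give no screener reply rate, ownership rate or expected split between the studies, so the rest uses assumed values.

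**What the indicator can measure.** The SAP does not define its ownership indicator. The only source of ownership data described is the screener:

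| Screener result | Study | Ownership |
|---|---|---|
| Answered yes | RCT 1 | Reported: yes |
| Answered no | RCT 2 | Reported: no |
| No reply in the window | RCT 2 | Unknown |

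A two-level indicator that follows study membership therefore separates *confirmed a smartphone* from *answered no or did not reply*.

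**Share of non-repliers in RCT 2.** Let r be the reply rate and s the share of repliers who own a smartphone. RCT 2 holds a fraction (1 − r) of non-repliers and r(1 − s) of patients who answered no, so

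w = (1 − r) / [(1 − r) + r(1 − s)].

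| r | s = 50% | s = 70% | s = 80% | s = 90% |
|---|---|---|---|---|
| 10% | 94.7% | 96.8% | 97.8% | 98.9% |
| 30% | 82.4% | 88.6% | 92.1% | 95.9% |
| 50% | 66.7% | 76.9% | 83.3% | 90.9% |
| 70% | 46.2% | 58.8% | 68.2% | 81.1% |
| 90% | 18.2% | 27.0% | 35.7% | 52.6% |

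For example, r = 90% and s = 50% gives 0.10 / (0.10 + 0.45) = 18.2%. With r = 10% and s = 90% it is 0.90 / (0.90 + 0.01) = 98.9%.

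**Share of owners in RCT 2.** If non-repliers own smartphones as often as repliers do (a further assumption), the share is w × s. Over s = 50–90% this is 23–73% at r = 70% and 41–86% at r = 30%.

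**What a pooled risk ratio can hide.** Assume w = 80%, with control acceptance of 5% among those who answered no and 2% among non-repliers. Pooled control acceptance is 0.2 × 0.05 + 0.8 × 0.02 = 0.026.

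- RR 1.5 in those who answered no and 1.0 in non-repliers: (0.2 × 0.05 × 1.5 + 0.8 × 0.02 × 1.0) / 0.026 = 0.0310 / 0.026 = 1.19.
- RR 1.0 and 1.3 respectively: (0.2 × 0.05 × 1.0 + 0.8 × 0.02 × 1.3) / 0.026 = 0.0308 / 0.026 = 1.18.

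Nearly the same pooled result thus fits a clear effect, or none, in people who said they have no smartphone.

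**The case against.** The strongest defence has four parts.

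- **The default is disclosed.** The protocol states it in item 6, repeats it in the study overview and defines RCT 2 as the remainder in item 9. The shorter account in the purpose section can be read as a summary. This stands. The misleading label is the SAP's, and nothing was concealed.
- **The comparisons are randomised within the group.** Triage precedes randomisation, so navigation and frequency effects are unbiased for the population the protocol defines. This stands too. The risk ratio is collapsible, so leaving screener response out of the model does not bias the randomised comparison.
- **The design is defensible.** Sending unconfirmed patients to text messaging is a rule that a clinic could use, and the mixed group is the one it would reach. Agreed. The triage rule itself needs no change.
- **The SAP draws no conclusion about people without smartphones.** It uses a label, names no between-study contrast among its primary hypotheses, and mentions the ownership indicator only in a preliminary check. This limits the point but does not remove it. The label carries two coprimary results, and nothing in the SAP tells a reader who is in the group.

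A reader might also infer that RCT 2 consists mainly of non-repliers, or mainly of smartphone owners. The documents do not support either, since neither rate is given and at a 90% reply rate the non-replier share could be as low as 18%. Nor do they show that non-repliers ignored a text message, because they do not state how the screener was delivered or how often.

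**Conclusion.** The point holds as one about estimand, labelling and generalisability. The RCT 2 results apply to patients who answered no or did not reply. They cannot be read as specific to people without smartphones, and any contrast between the studies confounds ownership with responsiveness. It would go too far to say that the results do not describe people without smartphones at all, since such people are in the group, or that the arm comparisons are biased.

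The existence of the default and the SAP's silence about it rest on the text alone. The size does not: the 18–99% range depends on assumed reply rates of 10–90% and assumed ownership of 50–90% among repliers. The owner shares further assume that ownership is unrelated to replying, and the pooled risk ratios are an illustration only. That screener response predicts acceptance is an inference from the shared dependence on a reply, and its strength is unknown.

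**What to change.** 1. In the SAP, rename RCT 2 along the lines of *no confirmed smartphone (answered no, or no reply to screener)*, state the reply window, and rename the ownership indicator to match.
2. Add the pre-randomisation screener response (answered no / no reply) as a covariate in the RCT 2 log-binomial models. The purpose is precision, not removal of bias. The SAP is written in the past tense and already reports preliminary findings, so declare this as an addition and also show the estimates without it.
3. Report counts by arm, acceptance proportions and risk ratios separately for the two screener groups, as descriptive or secondary results.
4. State RCT 1 conclusions as applying to patients who answered the screener and confirmed a smartphone.

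The cost is SAP wording, one binary covariate and one table. Triage needed the screener answer, so it should be available, although the documents do not say that no answer and a no are stored separately. Intervals may be wide in the smaller screener group: at r = 10% and s = 90%, those who answered no would number about 29,461 × 0.10 × 0.10 ≈ 295. The label becomes less simple. Alpha, sample size and randomisation stay as they are.

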Bear Lake Community Health Center: Bear Lake Community Health Center - Garden City, Box Elder Community

Health Center - Brigham City, Cache Valley Community Health Center - North Logan, Cache Valley Community Health Center - Providence

and Wasatch Homeless Health Care, Inc.: Fourth Street Clinic and Fourth Street Mobile Medical Clinic

Data will be collected via reports from the CHCs via the Association for Utah Community Health (AUCH). The University of Utah will administer text messaging/conversational agent interface and phone coaching. Patient randomization and data analysis will occur at the University of Utah.

The research team has verified that each participating clinic has a published Notice of Privacy Practice which states that patient's Protected Health Information (PHI) with patient identifiers can be disclosed for research without patient consent.

4. * Describe the medical or psychological resources available at this site (and other participating sites, if applicable) that participants might require as a consequence of the research. If not applicable, please state.

Not applicable.

5. * How will adverse events, unanticipated problems, interim results, and changes to the research be communicated between the participating sites and the Principal Investigator?

Any adverse events, unanticipated problems, interim results, and changes to the research will be communicated between participating sites and the principal investigator at weekly meeting attended by PI, CO-Is, project staff, and partner representatives including AUCH and UDOH. Pressing matters will be handled through direct communication from the PI, Program Manager, and participating sites via email, phone calls, or virtual meetings.

IRB_00150669

Created: 1/10/2022 7:14

AM

Documents and Attachments

PI: [name] MD,

Submitted: 3/21/2022

PhD

Title: SCALE UP Utah II: Community-Academic Partnership to Address COVID-19 Testing and Vaccination Among Utah Community Health Centers

Documents and Attachments

If any of your documents (such as investigational brochures, sponsor protocols, advertisements, etc.) are not available in an electronic format, please scan and save them as PDF files or contact our office for assistance.

IRB_00150669

Naming Documents: Please use the title field to clearly indicate the content of each form. The name you enter will be listed on your approval letter. Use names that will differentiate from earlier versions.

Examples:

Consent Document Control Group 04/14/05 Consent Document Treatment Group 4/14/05 Sponsor Protocol 04/14/05 Version 2 Assent Document(Highlighted Changes)

Apple/Macintosh Users:MS Word documents must have a .doc file extension. See ERICA home page for instructions.

Print View: IRB Draft Protocol Summary

eProtocol Summary:

Date Created Date Modified Name Version **Date Approved**

There are no items to display

Consent Documents, Consent Cover Letters, Consent Information Sheets, Consent Scripts, etc.:

Date Created Date Modified Date Approved Name Version

There are no items to display

Parental Permission Documents:

Name Version **Date Created Date Modified Date Approved**

There are no items to display

Assent Documents:

Name Version **Date Created Date Modified Date Approved**

There are no items to display

VA Consent Documents:

Name Version **Date Created Date Modified Date Approved**

There are no items to display

Surveys, Questionnaires, Interview Scripts, etc.:

Name Version **Date Created Date Modified Date Approved**

There are no items to display

Full Protocol (company protocol, sponsor protocol, investigator-initiated protocol, etc.):

Name Version **Date Created Date Modified Date Approved**

There are no items to display

Investigational Brochure (IB) for Investigational Drug or Drug/Device Package Insert:

Name Version Date Created Date Modified Date Approved

There are no items to display

Grant Application:

The Federal Government is a direct or indirect sponsor of your research. You are required to provide a copy of the grant proposal, grant award, or sub-award.

By submitting to the IRB, you are confirming the grant and the study protocol are consistent (Design, Study Population, Study Objectives and Goals, Test Interventions and Procedures, etc.)

Name Version Date Created Date Modified Date Approved

There are no items to display

Literature Cited/References:

Name Version Date Created Date Modified Date Approved

There are no items to display

Principal Investigator's Scholarly Record (CV/Resume):

Name	Version	Date Created	Date Modified	Date Approved
∠ CV(0.06)	0.06	1/12/2011 3:19 PM	2/3/2015 8:03 AM	
NIH Biosketch(0.04)	0.04	1/12/2011 3:20 PM	2/3/2015 8:05 AM	

Faculty Sponsor's Scholarly Record (CV/Resume):

Name Version Date Created Date Modified Date Approved

There are no items to display

Other Stamped Documents:

Name Version Date Created Date Modified Date Approved

There are no items to display

Recruitment Materials, Advertisements, etc.:

Name Version Date Created Date Modified Date Approved

There are no items to display

Other Documents:

Name Version Date Created Date Modified Date Approved

PI: [name] [name] Submitted: 3/21/2022

Title: SCALE UP Utah II: Community-Academic Partnership to Address COVID-19 Testing and Vaccination Among Utah Community Health

Centers

Finish Instructions

Finish Instructions

- 1. To view errors, select the "Validate" option at the top-left of the page. If you have errors on your application, you won't be able to submit it to the IRB.
- 2. Selecting the Finish button will NOT submit the application to the IRB.

 You MUST select the "Submit" option on the workspace once you've selected the "Finish" button.
- 3. If your study has a faculty sponsor: Once the PI submits the application, it will be sent to the faculty sponsor for final approval. The IRB cannot review the study until the faculty sponsor submits the application to the IRB.

Date: Thursday, September 5, 2024 3:42:17 PM

IRB_00150669 - AM_Adding AUCH as

study site; remove survey; remove NIH

Created:

10/18/2022 9:15 AM

Submitted:

11/2/2022

Title: SCALE UP Utah II: Community-Academic Partnership to Address COVID-19 Testing and Vaccination Among Utah

Community Health Centers

data transfer

PI: [name]

Print **AM 00046366**

1. Amendment Type

Close

1. Amendment Introduction

Brief Description of the Study: (This will populate from original application)

SCALE-UP II is a state-wide, pragmatic study conducted among 11 Community Health Center (CHC) systems and 38 clinics across Utah. These CHCs serve low socioeconomic status, racially/ethnically diverse, and rural/frontier populations. The long-term objective of SCALE-UP II is to increase the reach, uptake, and sustainability of COVID-19 testing among underserved populations. Through RADx-UP Phase I funding (SCALE-UP Utah), the team has established population health management (PHM) interventions that have been used since Jan 2021 to increase the uptake of COVID-19 testing and vaccination among CHC patients. Interventions are based on a PHM approach that uses widely available technology (i.e. cell phones and text messaging). SCALE-UP II will both build on SCALE-UP Utah PHM interventions and investigate novel interventions (i.e., Conversational Agents; Proactive vs. Reactive Patient Navigation) that are tailored to address individuals' hesitancy factors and that work at the interplay between vaccination and testing.

SCALE-UP II builds on long standing partnerships among the University of Utah Clinical and Translational Science Institute (UofU CTSI), Association for Utah Community Health (AUCH), CHCs, and the Utah Department of Health (UDOH). CTSI and SCALE-UP II investigators are leading several COVID-19 initiatives that drive public health response and state government policies in Utah. Thus, the UofU team is uniquely positioned to lead this project.

SCALE-UP II will implement and evaluate practical, accessible, and scalable PHM interventions to increase COVID-19 testing and vaccine uptake based on the best evidence available, patients' specific barriers and hesitancy factors, and extensive collaboration with CHCs, AUCH, and UDOH:

- 1. **Text Messaging (TM):** bidirectional text messaging to connect patients to vaccination or mailed at-home rapid test kits for use as needed.
- 2. **Conversational Agent (CA):** automated, scripted and interactive agent used to mimic human interaction to: 1) elicit specific hesitancy factors and barriers to testing; 2) provide individually tailored information to address hesitancy and barriers; and 3) offer a connection to mailed at-home rapid test kits.
- 3. **Patient Navigation (PN):** phone call from a community health worker to help address hesitancy and access barriers, and to offer at-home rapid test kits. Two types of PN will be tested: **Reactive PN** (RPN) will contact only those patients who reply YES to a TM/CA message. **Proactive PN** (PPN) will contact all patients regardless of their responding or not to the TM/CA messaging.

Prior to randomization, patients will be triaged into one of two studies based on self-reported ownership of a smart phone with internet access.

The primary outcome, Testing, captures whether patients actually test with the mailed at-home test kit.

Secondary outcomes include: *Time-To-Vaccine* (time-to-event outcome) as well as several implementation outcomes including *Reach-Engage Testing* (proportion of patients that reply to an offer to receive an at-home rapid test kit) and *Reach-Accept Testing* (proportion of patients that accept an offer to receive an at-home test kit). A similar set of implementation outcomes will be measured for vaccination (i.e., *Reach-Engage Vaccine* and *Reach-Accept Vaccine*).

1. Name of Amendment:

Use a name that will make it easy to identify the contents of the amendment. You may use

information such as the sponsor amendment number or an internal tracking number.

Adding AUCH as study site; remove survey; remove NIH data transfer

2. Type of Amendment (check all that apply):

Administrative changes:

Changes to study procedures:

Changes to consent, parental permission, or assent documents

Changes to the risk/benefit profile and/or participant safety parameters

3. Current Status of the Study:

Open for Enrollment

4. Total Number of Participants Enrolled To Date

At Utah: 0 All Centers: 0 IRB_00150669 - AM_Adding AUCH as study site; remove survey; remove NIH data transfer 10/18/2022 9:15

Created: AM_00046366 2. Description

AM

PI: [name]

Submitted: 11/2/2022

Title: SCALE UP Utah II: Community-Academic Partnership to Address COVID-19 Testing and Vaccination Among Utah Community

Health Centers

2. Amendment Description _

	You have indicated that t	the following types of	changes are being made:
--	---------------------------	------------------------	-------------------------

Administrative changes:

Changes to study procedures:

Changes to consent, parental permission, or assent documents

Changes to the risk/benefit profile and/or participant safety parameters

- 1. What changes are being made? List and number each change, grouping similar changes together.
 - 1. Administrative changes
 - a. We would like to add Association for Utah Community Health as a study site.
 - 2. Changes to study design and procedures:
 - a. We would like to remove the CDE survey administered by a survey company
 - b. We would like to remove the procedure for sending data to the NIH
- 2. Describe the reason for each of the changes described above. List and number the reasons according to the list above.
 - 1. Administrative changes
 - a. We need to add the Association for Utah Community Health (AUCH) as a study site because AUCH employs the community health workers who work as patient navigators for this study.
 - 2. Changes to study design and procedures
 - a. We need to remove the procedure for administering the CDE survey because we have not signed a contract or reliance agreement with a survey company yet. Our plan is to re-add this procedure once we have a contracted survey company.

Because we are removing the administration of the CDE survey for this amendment, we have also removed information on the consent process page as well as the risks and benefits page.

On the consent process page, we removed all consent language/processes that are tied to the CDE (3 month follow up) survey. This includes the online consent and the phone consent. We have left the waiver of consent language in the study because the waiver of consent is what allows for the review of patient's data at participating CHCs to establish cohort selection.

On the risks and benefits page, we have removed all of the details about the compensation that are linked to the CDE (3 month follow up) survey. The only compensation in this study is for the CDE (3 month follow up) survey, therefore this amendment aims to remove the compensation.

b. We need to remove the procedure for sending data to the NIH because we are waiting on details from the NIH regarding the secure handling and storage of these data. Once we receive these details, we will re-add this

	procedure and fill out the data banking section an	d add safe harbor for	sharing data.					
3.	How does each change described above affect participants? List and number the effects according to the above list.							
	1. Administrative changes will have no effect on p	articipants.						
	2. Changes to study design will not have any effect on participants because we have not enrolled any participants yet.							
4.	Will the modification(s), in the opinion of the local PI, increase or decrease the risk to participants? Neither							
	If the risk changes, provide justification:							
5.	How will enrolled participants (current and pas	st) be notified of this	change?					
	N/A - No currently enrolled participants							
	If Other, please explain:							
6.	Which approved documents are affected by the There are no items to display If other, please list: n/a	ese changes?						
7.	Which sections of the Update Study Application 2. Study Locations and Sponsors 4. Study Information- question 6 Consent Process 6. Risks and Benefits 7. HIPPA and the Covered Entity Information for Accounting of Disclosures	on are affected by the	ese changes?					
8.	Select all study locations that are affected by t	these changes.						
	Prior Approved Study Controlled Location	s						
	Site Name	Investigator Name	Covered Entity					
	☐ Association of Utah Community Health	[name]	Study procedures will be conducted within a HIPAA Covered Entity at this site (HIPAA Privacy Rule applies)					
	☐ University of Utah	[name]	Study procedures will be conducted within a HIPAA Covered Entity at this site (HIPAA Privacy Rule applies)					
	☐ Elite Research LLC (Irvine Texas)	[name]	Study procedures will be conducted within a HIPAA Covered Entity at this site (HIPAA Privacy Rule applies)					
	New Sites							

IRB_00150669 - AM_Adding AUCH as study site; remove survey; remove NIH data transfer

Created: AM_00046366

10/18/2022 9:15
AM_

3. Report Forms

PI: [name] Submitted: 11/2/2022

Title: SCALE UP Utah II: Community-Academic Partnership to Address COVID-19 Testing and Vaccination Among Utah Community Health Centers

2	D	on.	ort	E	rms
J.	п	CD	UΙL	ΓU	$_{\rm IIII}$

			10 II (D	reporting	policy 101	unanticipated
s and non-complia	nce?					
	s and non-complia	s and non-compliance?				

If yes, a Report Form must also be submitted and then linked to this amendment. Link the related report form to the amendment application by clicking 'Attach'. Then select the related Report Form from the list.

You can also submit a new Report Form from this amendment application by clicking 'New'. Follow the instructions for creating a new Report Form below.

ID Name Date Submitted Status

IRB_00150669 - AM_Adding AUCH as study site; remove survey;

Created: AM_00046366 10/18/2022 9:15 6. Docume AM

6. Documents and Attachments

PI: [name]

